2.9	Additional sample of toric lens orientation (1)	Instruction the subject to leave the consulting room and walk around for at least 2 minutes. Upon their return, measure and record the toric lens orientation to the nearest degree in each eye.															
2.10	Additional sample of toric lens orientation 2	Repeat the previous step once again.															
2.11	Lens removal	
Remove and place both lenses into a lens case with saline solution.
 
Do not discard the lenses until after biomicroscopy has been completed.
															
2.12	Biomicroscopy	
The FDA Slit Lamp Classification Scale will be used to grade findings. If any slit lamp finding is graded as 3 or worse, the subject must be discontinued, an adverse event will be recorded, and the subject will be monitored as per the guidelines given in section 13.
 
Should the clearance of the fluorescein need to be expedited, preservative-free rewetting drops or artificial tears may be instilled.
 
Study lenses may be discarded if there is no reason to store them following biomicroscopy.
															
2.13	Exit visual acuity	Record the exit monocular distance Snellen visual acuity for each eye with the subject wearing their habitual correction.															

Clinical Study Protocol
Johnson & Johnson Vision Care, Inc.

Visit 2: Follow-U #1		
Step	Procedure	Details
2.14	Schedule next visit	Schedule the next visit (Visit 3) to occur following a washout period of 7 ± 2 days (counting the day of this visit as day 0, the subject may return on day 5 through 9). Subjects may wear their habitual lenses during the washout period.

VISIT 3

Visit 3 will occur 5 to 9 days following Visit 2. Subjects may wear their habitual contact lenses to this visit.

Visit 3: Continuance		
Step	Procedure	Details
3.1	Review medical history and concomitant medications	Record any changes to the subject's medical history or concomitant medications.
3.2	Subject reported ocular symptoms	Record any subject reported ocular symptoms in response to a verbal open-ended symptoms questionnaire.
3.3	Entrance visual acuity	Record the entrance distance Snellen visual acuity for OD and OS with the subject wearing their habitual correction.
3.4	Remove habitual lenses (if worn)	If worn, the subject's habitual contact lenses will be removed. Lenses may be stored in a lens case, if required.
3.5	Biomicroscopy	The FDA Slit Lamp Classification Scale will be used to grade findings. If any slit lamp finding is graded as 3 or worse, the subject must be discontinued, an adverse event will be recorded, and the subject will be monitored as per the guidelines given in section 13. Should the clearance of the fluorescein need to be expedited, preservative free rewetting drops or artificial tears may be instilled.
3.6	Continuance	Verify that the subject is eligible to continue in the study.

Visit 3: Lens Fitting #2

The steps followed will be the same as those listed under Visit 1: Lens Fitting #1.

VISIT 4

Visit 4 will occur 5 to 9 days following Visit 3. Subjects must present to this visit wearing the study lenses in both eyes, and lenses must have been worn for at least 1 hour prior to the visit.

Subjects should bring their own habitual spectacles or contact lenses to this visit to wear following study lens removal.

Visit 4: Follow-Up #2

The steps followed will be the same as those listed under Visit 2: Follow-Up #1, up to and including step 2.12 'Biomicroscopy' ('Exit visual acuity' and 'Schedule next visit' will not be completed here). Additionally, a Preference Questionnaire will be completed as part of the Follow-Up PRO questionnaire (step 2.5).

Clinical Study Protocol
Johnson & Johnson Vision Care, Inc.

FINAL EVALUATION

The final evaluation will ordinarily take place immediately following the last scheduled follow-up visit per the study protocol. It may also take place at any point the subject discontinues the study or is terminated from the study.

Final Evaluation		
Ste	Procedure	Details
F.1	Subject Disposition	Indicate if the subject completed the study successfully. If the subject is discontinued from the study, indicate the reason.
F.2	Exit Refraction	Perform bare-eye subjective spherocylindrical refraction with a phoropter and record the best-corrected distance visual acuity (OD and OS) to the nearest letter. Note: This step is not necessary if the subject was exited due to screen failure.
F.3	Exit Slit Lamp Biomicroscopy (for subjects that are discontinued early)	FDA Slit Lamp Classification Scale will be used to grade the findings. If the clearance of the fluorescein needs to be expedited, preservative-free rewetting drops or saline may be instilled. This step is not necessary if the subject was exited due to screen failure. Note: This step is not necessary if the subject was exited due to screen failure, or if biomicroscopy was performed as part of the final follow-up visit procedures i.e., immediately prior to the final evaluation.

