2.2. Endpoints

Primary Safety Endpoints:

Slit Lamp Findings (SLF)

SLFs (Grade 3 or higher) related to study lens wear will be assessed for each eye at all study visits (scheduled and unscheduled). SLFs will be evaluated and graded using the FDA Grading scale from 0 to 4, where Grade 0 represents the absence of findings and 1 to 4 representing successively worse findings. The percentage of eyes with Grade 3 or higher SLF will be analyzed and will include corneal infiltrates. See [REDACTED] in Appendix D for more details on the collection of SLFs.

Acceptable Lens Fit

Acceptable lens fit will be assessed at all study visits (scheduled and unscheduled) for each subject eye. Acceptable fit is a binary response where Y=1 if lens fit is acceptable and Y=0 otherwise. Lens fit will be deemed unacceptable if any one of the following criteria are met:

- limbal exposure at primary gaze or with extreme eye movement;
- edge lift;
- excessive movement in primary up gaze;
- insufficient movement in all three of the following conditions: primary gaze, up gaze, and push up test.

Eyes with multiple unacceptable fitting events will be counted only once. See [REDACTED] in Appendix H for additional details regarding lens fit assessments.

Primary Efficacy Endpoints:

Visual Acuity (logMAR)

Visual acuity (VA) will be assessed monocularly at the 1-week follow-up evaluation under high-luminance high-contrast (HLHC) conditions at a test distance of 4 meters using ETDRS Charts. See [REDACTED] in Appendix D for details regarding the collection of visual acuity.

Toric Lens Orientation

Toric lens orientation (scribe mark position relative to 6 o'clock) will be assessed for each eye at 1, 3 and at least 15 minutes after lens insertion at the fitting visit, and at the 1-week follow-up visit. However, lens orientation at least 15 minutes after lens insertion at the fitting visit is the primary endpoint. Lens orientation is a binary response where Y=1 if the absolute lens orientation is $\leq 10^\circ$ and Y=0 otherwise. See [REDACTED] in Appendix D for details regarding the collection of absolute toric lens orientation.

Rotational Stability

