2.3. Hypotheses

Co-Primary Safety Hypotheses:

1. The percentage of eyes with one or more clinically significant, study-lens related, slit-lamp findings (Grade 3 or 4) following wear of the test lenses will be less than 5%.
2. At least 80% of lens fits will be acceptable at the dispensing visit.

Both co-primary *safety* hypotheses must be met in order to test any co-primary *efficacy* hypotheses.

Co-Primary Efficacy Hypotheses:

1. After approximately 1-week of wear, the mean monocular, high-luminance, high-contrast distance visual acuity for the test lens will be lower than 0.00 logMAR (equivalent to 20/20 Snellen visual acuity).
2. Following lens settling (at least 15 minutes) at the dispensing visit, at least 80% of lens fits will have absolute rotation less than or equal to 10 degrees.
3. Following lens settling (at least 15 minutes) at the dispensing visit, at least 80% of lens fits will have lens rotational stability with blink less than or equal to 5 degrees.
4. After approximately 1 week of wear, the mean overall CLUE™ Vision score for the test lens will be statistically greater than 62 points.

All safety and efficacy co-primary hypotheses must be satisfied in order to meet the study objectives and to test any secondary hypotheses.

Secondary Hypotheses:

1. After approximately 1 week of wear, the mean overall CLUE™ Handling score for the test lens will be greater than 61 points with 95% statistical confidence.
2. After approximately 1 week of wear, the mean overall CLUE™ Comfort score for the test lens will be greater than 58 points with 95% statistical confidence.

Clinical Study Protocol
Johnson & Johnson Vision Care, Inc.

Exploratory Hypotheses:

1. After approximately 1 week of wear, the test lens will be non-inferior to the control lens with respect to at least one of the following subjective questionnaire items asked at the follow-up visit:
 - a. Ability to see comfortably while driving during the day
 - b. My vision was clear enough to allow me to drive at night
 - c. Reduction in the feeling of tired eyes from using a computer or other digital device

A non-inferiority margin of 10% will be used.

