Visit 1: Lens Fittin #1		
Step	Procedure	Details
1.21	Toric fit assessment	
Record for each eye:
 
 1. The rotational position to the nearest degree 2. Lens stability with blinks 3. Toric fit acceptability. The toric lens fit will be designated as 'unacceptable' if either: 
 a. The lens ABSOLUTE ROTATION is greater than 20 degrees b. The LENS STABILITY WITH BLINK is greater than 5 degrees 
If one or both lenses demonstrate an unacceptable toric fit, the subject will be discontinued (proceed to final evaluation).

1.22	General lens fit assessment	
The fitting characteristics of the lens in both eyes will be assessed using a slit lamp. Lens position (centration, limbal exposure, edge lift) and movement (primary and up gaze as well as push-up) will be assessed. Fit acceptability is defined as any lens that does not display the following general fit characteristics:
 
 • Limbal exposure (presence of clear comea) in any direction of gaze. • Edge lift. • Insufficient movement in all three movement assessments (primary gaze, up-gaze and push-up test). • Excessive movement in primary gaze. 
If the general fit is unacceptable for either eye, the subject will be discontinued (proceed to exit evaluation).

1.23	Spherical over-refraction	
Perform monocular spherical over-refraction using duo-chrome to refine the endpoint as described in step 1.11 (the final spherical endpoint may be determined binocularly).
 
The spherical over-refraction must be plano in both eyes to continue.
 
If a non-plano over-refraction is found in either eye, the lens(es) must be refit with the indicated change in sphere power. If the indicated lens power is not available for either eye (e.g., outside the available SKU range), the subject will be discontinued (proceed to final evaluation).

Clinical Study Protocol
Johnson & Johnson Vision Care, Inc.

Visit 1: Lens Fittin #1		
Step	Procedure	Details

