8.2. Withdrawal/Discontinuation from the Study

A subject will be withdrawn from the study for any of the following reasons:

- Subject withdrawal of consent.
- Subject not compliant to protocol.

Clinical Study Protocol
Johnson & Johnson Vision Care, Inc.

- Subject lost to follow-up.
- Subject no longer meets eligibility criteria (e.g. the subject becomes pregnant).
- Subject develops significant or serious adverse events necessitating discontinuation of study lens wear.
- Subjects who have experienced a Corneal Infiltrative Event (CIE).
- Investigator's clinical judgment regarding the subject safety reasons (that it is in the best interest of the subject to stop treatment).
- Subject missed any study visits
- Subject not compliant with study lens wear schedule.
- Subject not successfully dispensed due to lack of efficacy and safety including poor vision, poor comfort, or unacceptable fit.

For discontinued subjects, the Investigator will:

- Complete the current visit (scheduled or unscheduled).
- Complete the Final Evaluation, indicating the reason that the subject was discontinued from the study.
- Record the spherocylindrical refraction with best corrected distance visual acuity.
- Collect used test article(s) (worn or brought to the visit) from the subject and discard them, unless otherwise stated in section 7.2.
- Collect all unused test article(s) from the subject.
- Make arrangements for subject care, if needed, due to their study participation

Additional subjects may be enrolled if a subject discontinues from the study prematurely.

In cases where a subject is lost to follow-up, every possible effort must be made to contact the subject and determine the reason for discontinuation/withdrawal. The measures taken to follow up must be documented including two written attempts and a certified letter (or equivalent) as the final attempt.

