Grade 3 or Higher Slit Lamp Findings (SLFs)

Grade 3 or Higher SLFs related to study lens wear will be converted to a binary response as $YY = 1$, if a subject eye has a clinically significant SLF, and $YY = 0$ otherwise, for analysis purposes. From the historical data there was *none or an extremely low rate* ($< 1\%$) for clinically significant SLFs (Grade 3 or higher) for the test lens. Assuming a correlation of 0.70 between left and right eyes within the same subject, a total of 5000 replicating trials were simulated with a reference rate of 2% (worse-case scenario). Given the rare event binary outcome of slit lamp findings, each replicated sample was analyzed using a Bayesian beta-binomial model with correlated binary data (Diniz et al; 2010).⁸ For each simulated trial, the upper bound of the 95% central posterior credible interval constructed for the percentage of grade 3 or higher SLFs for the test lens was compared to a margin of 5%. With the proposed sample size, at least 99% of the estimated 95% credible intervals had the upper bound below 5%.

Acceptable Lens Fitting

Acceptable lens fitting will be converted to a binary response as $YY = 1$, if a subject eye has acceptable lens fitting, and $YY = 0$ otherwise, for analysis purposes. As indicated in the historical data of these lenses there was an extremely high rate ($> 99\%$) acceptable lens fitting for the test lens. Assuming a correlation of 0.70 between left and right eyes within the same subject, a total of 5000 replicating trials were simulated with a reference rate of 99% (worse-case scenario). Given the rare event binary outcome of $Y=0$ (unacceptable lens fitting), each replicated sample was analyzed using a Bayesian beta-binomial model with correlated binary data (Diniz et al; 2010).⁸ For each simulated trial, the upper bound of the 95% central posterior credible interval constructed for the percentage of acceptable lens fittings for the test lens was compared to a margin of 80%. With the proposed sample size, at least 99% of the estimated 95% credible intervals had the lower bound above 80%.

Co-Primary Efficacy Endpoint Sample Size Calculations:

Distance Monocular Visual Acuity (logMAR) and CLUE Vision Scores

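### Step 1.21 sends a subject out on a failed toric fit before step 1.22 records general lens fit, in conflict with sections 8.2 and 2.2, so the lens-fit safety co-primary may be missing for both eyes

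*Combined protocol and SAP*

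**What the plan says.** Section 7.2, Visit 1, step 1.21 records rotation and stability with blinks for each eye. It calls the toric fit unacceptable if rotation exceeds 20 degrees or stability with blinks exceeds 5 degrees, and continues: "If one or both lenses demonstrate an unacceptable toric fit, the subject will be discontinued (proceed to final evaluation".

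General fit comes next, at step 1.22: "The fitting characteristics of the lens in both eyes will be assessed using a slit lamp". This is the only visible step that collects limbal exposure, edge lift and movement, which define the acceptable-fit endpoint in section 2.2. Step 1.22 carries its own discontinuation instruction. For Visit 3, section 7.2 says "The steps followed will be the same as those listed under Visit 1: Lens Fitting #1", so the order repeats in period 2.

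The Final Evaluation has three items: disposition (F.1: "Indicate if the subject completed the study successfully. If the subject is discontinued from the study, indicate the reason"), refraction (F.2) and slit lamp examination (F.3). None is a lens-fit grade.

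Two other sections point the other way. For discontinued subjects, section 8.2 lists first "Complete the current visit (scheduled or unscheduled", ahead of the Final Evaluation. Section 2.2 says "Acceptable lens fit will be assessed at all study visits (scheduled and unscheduled) for each subject eye".

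The hypothesis in section 2.3 is "At least 80% of lens fits will be acceptable at the dispensing visit". It is one of two safety hypotheses that must both be met before any efficacy hypothesis is tested. Section 14.5 analyses it on the safety population. Section 14.9 rules out imputation and plans multiple imputation as a sensitivity analysis only if dropout exceeds 15%.

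**The concern.** A subject who leaves at step 1.21 has had the lens on the eye, so belongs to the safety population, but may have no value for an endpoint analysed there. One failing eye takes the fellow eye's result with it. Sites that follow step 1.21 and sites that follow section 8.2 would produce different data from the same kind of subject. The visible text of section 14 has no rule for an eye fitted but not graded; a stand-alone SAP is announced but is not part of the document.

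The missingness is triggered by another fit result on the same lens, so it cannot be presumed unrelated to the endpoint. If lenses that rotate or are unstable also tend to fit poorly in general, the observed acceptable percentage would be too high. At stake is the credibility of a gate in front of all efficacy testing.

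**Working it through.** **Inputs.** From section 14.2: reference rate for acceptable fit (trials "were simulated with a reference rate of 99% (worse-case scenario"), between-eye correlation ρ = 0.70, threshold 80%, reference rates 97.5% for orientation within 10 degrees and 98% for stability within 5 degrees. Table 8 gives historical values of 100% acceptable fit, 97.5% orientation and 100% stability. Table 9 gives N = 100 and 99% power for lens fit. Section 4.3 gives 180 enrolled and 165 completing.

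**Model.** Section 14.5's correlated-binomial mixture, for a per-eye success rate p:
- both eyes succeed: ρp + (1−ρ)p²
- exactly one succeeds: 2(1−ρ)p(1−p)
- neither succeeds: ρ(1−p) + (1−ρ)(1−p)²

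At p = 0.99 these are 0.98703, 0.00594 and 0.00703. Posterior intervals use the stated priors (normal with variance 1000 on the logit, Beta(0.5, 0.5) on ρ) for a single lens.

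**1. The plan's own figure.** In 5000 simulated trials at N = 100 and p = 0.99, the lower bound of the 95% central credible interval exceeded 0.80 in essentially 100%. The stated figure is at least 99%, so it reproduces.

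**2. How many subjects would leave at step 1.21.** With per-eye toric failure rate q, the share with at least one failing eye is 1 − [ρ(1−q) + (1−ρ)(1−q)²].
- q = 0 (historical stability): 0 subjects.
- q = 0.02 (protocol worst case for stability): 1 − [0.7×0.98 + 0.3×0.9604] = 0.0259, or 4.7 of 180 subjects and about 9 of 360 eyes.
- q = 0.045 (2% plus 2.5% with rotation above 10 degrees): 1 − [0.7×0.955 + 0.3×0.912025] = 0.0579, or 10.4 of 180 subjects and about 21 of 360 eyes. This is a deliberate ceiling, since step 1.21 uses 20 degrees, not 10.

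**3. Effect on the 80% test.** Treat all 180 as fitted with the test lens. Among those graded, take one subject with both eyes unacceptable and one with a single unacceptable eye (about 99% acceptable). Then compare ignoring the lost eyes with counting every one as unacceptable.

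| Lost of 180 | Interval, lost eyes ignored | Rate, all lost eyes unacceptable | Interval |
|---|---|---|---|
| 5 | 0.976 to 0.999 | 347/360 = 96.4% | 0.935 to 0.986 |
| 11 | 0.975 to 0.999 | 335/360 = 93.1% | 0.891 to 0.963 |
| 25 | 0.973 to 0.999 | 307/360 = 85.3% | 0.799 to 0.900 |

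The lower bound first falls to 0.80 or below at 25 of 180 (13.9%), or 23 of 165 (13.9%).

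**4. Whether another planned check would catch a loss of that size.** A per-eye failure rate of 11% gives 1 − [0.7×0.89 + 0.3×0.7921] = 0.139, the same 13.9%. On its own that is below the 15% trigger. With a true stability rate of 89% and 165 subjects, the stability co-primary would still exceed its 80% threshold in about 92% of simulated trials with a cluster-robust interval, and about 94% with the Bayesian model. Neither check would reliably flag it.

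**The case against.** The strongest reply is that this is a wording conflict, not a hole. Section 8.2 tells the investigator to complete the visit, section 2.2 requires the grade, and Table 3 marks general fit at Visits 1 and 3 without conditions. The loss would also be visible: step 1.21 records the toric failure, F.1 the reason for leaving, and section 14.9 reports missing counts, so it can be bounded afterwards. A subject who fails only after a refit under step 1.24 already has a general-fit record from the earlier lens. The Lens Fitting Characteristics and Toric Fit Evaluation work instructions are blacked out and may require both assessments together. All of this stands, and it limits the point to a conflict that needs reconciling.

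A reader might infer that the subjects lost are those most likely to fit poorly. The documents do not say so. The acceptable-fit criteria contain no rotation or blink-stability item. The control lens package insert groups excessive movement with the blink with limbal exposure and edge stand-off as signs of a flat fit, but does not mention rotation. Upward bias is plausible, not shown.

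A reader might also infer a seriously inflated false-pass rate. Suppose the true rate is exactly 80% and only unacceptable eyes are lost. Losing 25% or 50% of them moves the observed rate to 0.80/(0.80 + 0.20×0.75) = 84.2% or 0.80/(0.80 + 0.20×0.50) = 88.9%. With 165 subjects and a cluster-robust interval, the test then passes about 30% or 92% of the time. Those figures rest wholly on that extreme pairing, which nothing in the documents supports; with no association between the two fit results there is no bias.

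**Conclusion.** The point holds as a conflict between step 1.21 and sections 8.2 and 2.2 that leaves collection of a gating safety co-primary to each site's reading. It does not show that the endpoint goes unrecorded, nor which way any bias runs.

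Under the protocol's own rates, about 0 to 10 of 180 subjects (0 to 6%) would be affected. Even with every lost eye counted as unacceptable, the lower bound stays at about 0.89, so the 80% decision does not change. Reversal needs about 14% of subjects lost, all counted as failures. That is unlikely, but a loss of that size would not by itself trigger the planned sensitivity analysis.

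These figures assume a between-eye correlation of 0.70, about 99% acceptable fit among graded eyes, and all 165 or 180 subjects fitted with the test lens. The case for acting rests on the low cost of preventing an outcome-dependent gap, not on a threat to the expected conclusion.

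**What to change.** Reconcile step 1.21, and the matching exit in step 1.22, with sections 8.2 and 2.2. State that both the toric fit (1.21) and the general fit (1.22) are recorded for both eyes before a subject leaves for final evaluation, at Visits 1 and 3, and set up the eCRF to match. Say in the analysis section how any fitted eye without a grade is handled; counting such eyes as unacceptable gives a simple bound.

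Do not simply swap the two steps. Step 1.22 also discontinues, so a general-fit failure could then leave before settled orientation and blink stability, two efficacy co-primaries, are recorded.

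The discontinuation criteria are unchanged. The cost is a line or two of protocol text, an eCRF check, and an estimated extra minute at the slit lamp for the few subjects affected.
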